9.4.1.4 Management of Posterior Reversible Leukoencephalopathy Syndrome/
 Reversible Posterior Leukoencephalopathy Syndrome

Posterior Reversible Leukoencephalopathy Syndrome/ Reversible Posterior Leukoencephalopathy Syndrome (PRES/RPLS) is a neurological disorder that can present with headache, seizure, lethargy, confusion, altered mental function, blindness, and other visual or neurological disturbances. Mild to severe hypertension may be present. MRI is necessary to confirm the diagnosis of PRES/RPLS. Appropriate measures should be taken to control BP. In subjects with signs or symptoms of PRES/RPLS, the Dose Modification Guidelines (Table 5) should be followed.

9.4.1.5 Management of Proteinuria

Regular assessment for proteinuria should be conducted as detailed in the Schedule of Assessments (Table 7 and Table 8). Guidelines for assessment and management of proteinuria are summarized as follows:

1. Grading according to CTCAE v4.03 will be based on the protein-creatinine ratio, and whenever possible, also on the 24-hour urinary protein result per investigator's

discretion. Management of study treatment administration will be based on the grade of proteinuria according to the Dose Modification Guidelines.

2. A spot protein-creatinine ratio test, and if possible a 24-hour urinary protein test as per investigator's discretion, to verify the grade of proteinuria is required in the following situations:
 - The first (initial) occurrence of $\geq 2+$ proteinuria on urine dipstick while on study treatment
 - A subsequent increase in severity of urine dipstick proteinuria occurring on the same lenvatinib/everolimus dose level
 - When there has been a lenvatinib/everolimus dose reduction and at the new dose level the urine protein dipstick result is 2+, 3+, or 4+
3. Urine dipstick testing for subjects with proteinuria $\geq 2+$ should be performed every 2 weeks (or on Day 1 and Day 15 or more frequently as clinically indicated) until the results have been 1+ or negative for 3 consecutive months.
4. In the event of nephrotic syndrome, lenvatinib must be discontinued.

9.4.1.6 Management of Diarrhea

An anti-diarrheal agent should be recommended to the subject at the start of study treatment and subjects should be instructed and educated to initiate anti-diarrheal treatment at the first onset of soft bowel movements. The choice of anti-diarrheal agent should be individualized to the subject's clinical circumstances and follow standard medical practice. If signs/symptoms of diarrhea persist despite optimal medical management, instructions contained in the Dose Modification Guidelines should be followed.

9.4.1.7 Management of Non-Infectious Pneumonitis

Non-infectious pneumonitis is a recognized class effect of rapamycin derivatives, including everolimus. Non-infectious pneumonitis was described in 19% of subjects taking everolimus ([Afinitor package insert](#)). Some cases were severe and on rare occasions, a fatal outcome was observed. Investigators should therefore consider a diagnosis of non-infectious pneumonitis in subjects presenting with non-specific respiratory signs and symptoms and in whom infectious, neoplastic and other non-medicinal causes have been excluded by means of appropriate investigations.

Subjects who develop radiological changes suggestive of non-infectious pneumonitis and have few or no symptoms (Common Terminology Criteria for Adverse Events [CTCAE] Grade 1) may continue study dosing without dose adjustments.

1. If symptoms are moderate (CTCAE Grade 2):
 - Study treatment (lenvatinib-everolimus combination) should be interrupted and the use of corticosteroids may be indicated until symptoms abate (resolved to CTCAE Grade 0-1) and may then be restarted at the same doses prior to study treatment interruption.

- If Grade 2 non-infectious pneumonitis recurs despite optimal management, then study treatment administration should be interrupted and the use of corticosteroids may be indicated until symptoms abate (resolved to CTCAE Grade 0-1).
2. If symptoms are severe (CTCAE Grade 3):
 - Study treatment should be interrupted and the use of corticosteroids may be indicated until clinical symptoms resolve (to CTCAE Grade 0-1).
 3. If symptoms are life-threatening (CTCAE Grade 4):
 - Study medications should be discontinued.

9.4.1.8 Management of Infections

Everolimus has immunosuppressive properties and may predispose subjects to infections. It is important therefore to monitor for signs and symptoms of infection, and treat promptly. Dose alterations of everolimus may be required in accordance with everolimus prescribing information, ie, Afinitor Disperz package insert or Votubia Summary of Product Characteristics (SmPC).

9.4.1.9 Management of Blood Glucose and Lipids

Hyperglycemia, hyperlipidemia and hypertriglyceridemia are recognized class effects of rapamycin derivatives, including everolimus. Glycemic and lipid control should be optimized before starting a subject on this study. Blood glucose will be monitored as specified in the Schedule of Procedures/Assessments. For subjects with blood glucose >ULN, a fasting (>6 hour, water only) blood glucose sample will be obtained. Grading will be based on the fasting blood glucose result. The choice of hypoglycemic agent should be individualized to the subject's clinical circumstances and follow standard medical practice.

Dose alterations of everolimus may be required in accordance with everolimus prescribing information, ie, Afinitor Disperz package insert or Votubia SmPC.

9.4.1.10 Management of Hepatotoxicity

Regular monitoring of liver function tests (ALT, AST, bilirubin levels) should be conducted as detailed in the Schedule of Assessments ([Table 7](#) and [Table 8](#)) and as clinically indicated. If signs/symptoms indicating liver injury occur, instructions contained in the table for dose reduction and interruptions of the protocol should be followed (see [Table 5](#)), for Study Treatment Dose Reduction and Interruption Instructions). Appropriate supportive care should be provided together with close monitoring. If hepatic failure occurs the study treatment must be discontinued.

9.4.1.11 Management of Thromboembolic Events

Subjects should be advised to pay attention to symptoms suggestive of venous thromboembolic events which include acute onset of shortness of breath, dyspnea, chest pain, cough, hemoptysis, tachypnea, tachycardia, cyanosis, deep vein thrombosis signs including lower-extremity swelling, redness and warmth to touch or tenderness. In case any of these symptoms appear, subjects should be instructed to report such symptoms promptly to the

treating physician. If a thromboembolic event is confirmed, instructions contained in the table for dose reduction and interruptions of the protocol should be followed, (see [Table 5](#)), for Study Treatment Dose Reduction and Interruption Instructions). Appropriate supportive care should be provided together with close monitoring. If a subject experiences life-threatening (Grade 4) thromboembolic reactions, including pulmonary embolism, the study treatment must be discontinued. If a subject experiences an arterial thromboembolism event of any grade, lenvatinib must be discontinued.

9.4.1.12 Management of Hypocalcemia

Serum calcium should be monitored per the Schedule of Assessments. Corrected serum calcium should be used to assess the grade of hypocalcemia per CTCAE v 4.03, using the following formula:

$$\text{Corrected calcium} = ([4 - \text{serum albumin in g/dL}] \times 0.8 + \text{serum calcium})$$

The formula is not applicable when serum albumin concentration is normal (>4 g/dL); in such situations, the total (uncorrected) serum calcium should be used instead.

Hypocalcemia should be treated per institutional guidelines (eg, using appropriate calcium, magnesium, and Vitamin D supplementation) until resolution.

9.4.1.13 Management of Hemorrhage

For subjects with hemorrhage, either resume at a reduced dose or discontinue study treatment depending on the severity and persistence of hemorrhage.

9.4.1.14 Management of Gastrointestinal Symptoms and Acute Abdominal Pain

Initial management of acute abdominal pain in these study subjects should be focused on treating the underlying cause where possible, ensuring appropriate hydration/rehydration, and symptomatic pain improvement consistent with subject's age and in accordance to local and institutional standards of care. Appropriate supportive care should be provided together with close monitoring.

For AEs of abdominal pain believed related to lenvatinib or more specific AEs believed related to lenvatinib that result in the symptom of abdominal pain, instructions contained in [Table 5](#) regarding study treatment dose reduction and interruption instructions. For Grade 4 AEs that result in abdominal pain, study treatment must be discontinued.

Gastrointestinal symptoms including diarrhea should be managed by providing symptomatic treatment. If the symptoms persist (eg, diarrhea for more than 10 days), Study Treatment Interruption and Reduction guideline should be followed. Gastrointestinal symptoms should be monitored closely and evaluated using CT, Contrast-Enhanced MRI, ultrasound, or other diagnostic imaging if clinically indicated, at the investigator's discretion. It is recommended that all gastrointestinal symptoms should be recorded in the diary provided.

9.4.1.15 Management of Fistula Formation and Gastrointestinal Perforation

Lenvatinib should be discontinued in any subject who develops Grade 4 fistula (gastrointestinal or non-gastrointestinal), or gastrointestinal perforation of any grade.

9.4.1.16 Management of Osteonecrosis of the Jaw

Perform an oral examination prior to treatment with lenvatinib and periodically during lenvatinib treatment. Advise study subjects regarding good oral hygiene practices. Avoid invasive dental procedures, if possible, while on lenvatinib treatment, particularly in study subjects at higher risk. For study subjects requiring invasive dental procedures, discontinuation of bisphosphonate treatment may reduce the risk of osteonecrosis of the jaw. Withhold lenvatinib if osteonecrosis of the jaw develops and restart based on clinical judgement of adequate resolution (see [Section 9.4.7](#)).

9.4.1.17 Management of QT Prolongation

Lenvatinib should be withheld in the event of development of QT interval prolongation greater than 500 msec. Lenvatinib should be resumed at a reduced dose when QTc prolongation is resolved to <480 msec or baseline. Monitor potassium, calcium and magnesium, and replenish as appropriate.

9.4.2 Identity of Investigational Products

The study drugs under evaluation in this study are lenvatinib in combination with everolimus. The sponsor will provide the study drugs packaged as open-label supplies.

Lenvatinib

[figure not shown]
Lenvatinib will be supplied by the sponsor in labeled containers. The sponsor will package lenvatinib as open-label supplies. Lenvatinib will be provided to the sites as #4 size hydroxypropyl methylcellulose (HPMC) capsules in 3 strengths differentiated by color (iron oxide red and iron oxide yellow); 1-mg capsule (yellowish red cap and white body, containing 1 mg E7080 anhydrous-free base), 4 mg capsule (yellowish-red cap and body, containing 4 mg E7080 anhydrous-free base); and 10 mg capsule (yellowish-red cap with yellow body, containing 10 mg E7080 anhydrous-free base). Excipients of the E7080 formulation will be calcium carbonate, mannitol, microcrystalline cellulose, hydroxypropylcellulose, low-substituted hydroxypropylcellulose, talc, hypromellose, titanium dioxide, iron oxide yellow, and iron oxide red. Lenvatinib capsules may be suspended in water or apple juice for children unable to swallow capsules. [Appendix 12](#) provides instructions for the preparation of the lenvatinib suspension.

Everolimus

Everolimus dispersible tablets for oral suspension will be provided as commercial drug product such as 'Afinitor Disperz' or 'Votubia dispersible tablets' in strengths of 2 mg, 3 mg, and 5 mg. Note that everolimus tablets contain lactose.

9.4.2.1 Chemical Name, Structural Formula of Lenvatinib

- Study drug code: E7080
- Generic name: lenvatinib
- Chemical name: 4-[3-Chloro-4-(*N'*-cyclopropylureido)phenoxy]-7-methoxyquinoline-6-carboxamide methanesulfonate
- Molecular formula: C₂₁H₁₉ClN₄O₄•CH₄O₃S
- Molecular weight: 522.96
- Structural formula:

9.4.2.2 Chemical Name, Structural Formula of Everolimus

- Generic name: everolimus
- Chemical name: -O-(2-hydroxyethyl)-rapamycin
- Molecular formula: C₅₃H₈₃NO₁₄

Refer to the latest everolimus prescribing information, ie, Afinitor Disperz package insert or Votubia SmPC.

9.4.2.3 Comparator Drug

Not applicable

9.4.2.4 Labeling for Study Drug

Lenvatinib and everolimus will be labeled in accordance with text that is in full regulatory compliance with each participating country and is translated into the required language(s) for each of those countries.

9.4.2.5 Storage Conditions

Study drug will be stored in accordance with the labeled storage conditions. Temperature monitoring is required at the storage location to ensure that the study drug is maintained within an established temperature range. The investigator or designee is responsible for ensuring that the temperature is monitored throughout the total duration of the study and that records are maintained; the temperature should be monitored continuously by using either an

in-house validated data acquisition system, a mechanical recording device, such as a calibrated chart recorder, or by manual means, such that minimum and maximum thermometric values over a specific time period can be recorded and retrieved as required.

9.4.3 Method of Assigning Subjects to Treatment Groups

This is an open-label, single-arm study. All subjects who provide signed informed consent to participate in this study and satisfy all eligibility requirements (see [Section 9.3](#)) will be assigned to receive lenvatinib in combination with everolimus in 28-day treatment cycles. There is no randomization in this study.

9.4.4 Selection of Doses in the Study

The purpose of the Phase 1 portion of the study is to determine the MTD and the RP2D of lenvatinib administered in combination with everolimus in this pediatric population. The dose levels of lenvatinib and everolimus to be evaluated in the study are pre-specified. The starting dose level of lenvatinib is 11 mg/m², which is approximately 80% of lenvatinib single dose MTD in pediatric subjects determined in the ongoing Study E7080-G000-207. The initial dose of everolimus is 3 mg/m², which is 66% of the FDA approved dose and dose previously found effective in subependymal giant cell astrocytoma.

9.4.5 Selection and Timing of Dose for Each Subject

Lenvatinib and everolimus are to be administered orally once a day at approximately the same time without regard to food intake for 28 days from Cycle 1 onward. If a subject misses a dose of lenvatinib, it may be taken within the 12 hours following the usual time of the dose. If more than 12 hours have elapsed from the time of the usual daily dose, lenvatinib should be taken the next day at the usual time. In the event a subject vomits after study drug administration, the subject should not take another dose until the next scheduled dose.

Refer to everolimus prescribing information for recommended everolimus dosing information.

Study drugs should be administered at the clinic on PK sampling days. All scheduled visits must be conducted as per protocol, irrespective of treatment interruption. If holidays or personal schedules make administration impossible on the scheduled days, then administration should be resumed as soon as possible.

9.4.6 Blinding

The study will not be blinded.

9.4.7 Prior and Concomitant Therapy

All prior medications (including over-the-counter medications) administered 28 days before the first dose of study drug and any concomitant therapy administered to the subject during

the course of the study (starting at the date of informed consent) until 28 days after the final dose of study drug will be recorded. Additionally, all diagnostic, therapeutic, or surgical procedures relating to malignancy should be recorded. Any medication that is considered necessary for the subject's health and that is not expected to interfere with the evaluation of or interact with the study medication may be continued during the study.

Aspirin, nonsteroidal anti-inflammatory drugs (NSAIDs), and low-molecular-weight heparin (LMWH) are permissible but should be used with caution. Erythropoietic stimulating agents (ESAs) may be used according to the American Society of Clinical Oncology (ASCO), institutional, or national guidelines and according to the SmPC or local labeling instructions, but the subject should be carefully monitored for increases in red blood cell counts.

Treatment (including blood products, blood transfusions, fluid transfusions, antibiotics, and antidiarrheal drugs, etc) of complications of AEs or therapy to ameliorate symptoms may be administered at the discretion of the investigator, unless it is expected to interfere with the evaluation of (or to interact with) the study medication.

An anti-diarrheal agent should be recommended to the subject at the start of study treatment and subjects should be instructed and educated to initiate anti-diarrheal treatment at the first onset of soft bowel movements. The choice of anti-diarrheal agent should be individualized to the subject's clinical circumstances and follow standard medical practice. If signs/symptoms of diarrhea persist despite optimal medical management, instructions contained in the Dose Modification Guidelines should be followed.

Administration of corticosteroids for progressive disease is not permitted. Administration of corticosteroids will be limited to premedication or the short-term treatment of acute medical conditions in accordance with approved indications, institutional, or national guidelines.

Palliative radiotherapy of up to 2 painful pre-existing, non-target bone metastases will be permitted without being considered progressive disease. In the Phase 1 part, palliative radiotherapy will be allowed after the completion of Cycle 1.

If a subject receiving treatment with lenvatinib requires surgery during the study, the stop time and restart time of lenvatinib should be as follows:

- For minor procedures: stop lenvatinib at least 2 days before the procedure and restart it at least 2 days after, once there is evidence of adequate healing and no risk of bleeding.
- For major procedures: stop lenvatinib at least 1 week (5 half-lives) prior to surgery and then restart it at least 1 week after, once there is evidence of adequate healing and no risk of bleeding.
- For scheduled dental surgery or invasive dental procedures: stop lenvatinib for at least 1 week before the procedure, then restart lenvatinib when deemed clinically appropriate.

If concomitant medication/therapy is administered for an AE, investigators will record that AE on the Adverse Events CRF.

9.4.7.1 Drug-Drug Interactions

Lenvatinib's weak in vitro inhibitory and induction potential on CYP enzymes (Study No. XT063020) suggests a low risk of lenvatinib interference with the PK of other drugs metabolized by CYP enzymes which are co-administered in usual clinical practice. Nonclinical studies identify CYP3A4 as the important CYP isozyme responsible for human hepatic metabolism of lenvatinib. However, clinical studies conducted showed that coadministration of lenvatinib with CYP3A4/P-gp inhibitors or inducers is not of clinical concern. The main metabolic pathways for lenvatinib in humans were identified as enzymatic (CYP3A and aldehyde oxidase) and non-enzymatic processes ([Lenvima[®] package insert](#)).

For subjects receiving everolimus, drugs or substances (including herbal supplements or grapefruit juice) known to be potent inhibitors of CYP3A4/P-gp should not be used. Potent inducers of CYP3A4/P-gp should not be used unless there is no alternative treatment available. Dose increase of everolimus may be considered when co-administering strong CYP3A4 or P-gp inducers. Moderate/ weak inhibitors or inducers or substrates of CYP3A4 and/or P-gp should be used with caution. Dose reduction of everolimus may be considered when co-administering moderate CYP3A4 or P-gp inhibitors. For further information, please refer to everolimus prescribing information.

9.4.7.2 Prohibited Concomitant Therapies and Drugs

Subjects are prohibited from receiving the following therapies during the Screening and Treatment Phase of this study:

- Concurrent anticancer therapies such as chemotherapy, TKIs, radiotherapy (with the exception of palliative radiotherapy as specified in [Section 9.4.7](#)), antitumor interventions (surgical resection, surgical debulking of tumor, etc), or cancer immunotherapy
- Concurrent other investigational drugs
- Live vaccines are prohibited while participating in the study. Examples of live vaccines include, but are not limited to, the following: measles, mumps, rubella, chicken pox, yellow fever, rabies, BCG, and typhoid (oral) vaccine. Seasonal influenza vaccines for injection are generally killed virus vaccines and are allowed. However intranasal influenza vaccines (eg, Flu-Mist[®]) are live attenuated vaccines, and are not allowed.

For subjects who, in the assessment by the investigator, require the use of any of the aforementioned treatments for clinical management, continuation of the study medication and further participation in the study must be discussed and agreed upon with the sponsor.

If subjects receive additional anticancer therapies, this will be judged to represent evidence of disease progression, and study medication will be discontinued. These subjects should complete all off-treatment assessments and continue to be followed for survival in the Follow-Up Period.

Further information on the prohibited concomitant therapies for lenvatinib and everolimus is included in the respective prescribing information.

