Determination of a DLT will be made by the investigator and the Eisai Medical Monitor in consultation with the PSC, as needed. Subjects who discontinue the study treatment for any reason other than DLT (eg, early disease progression) during Cycle 1 (Day 1 to Day 28), and have not received at least 75% of the prescribed dose prior to discontinuation, will be replaced.

The sponsor and PSC will review all subjects' safety and clinical data to jointly determine the MTD/RP2D of the combination of lenvatinib with everolimus. The Treatment Phase for each subject in Phase 1 ends after completing Cycle 1 of treatment unless subject discontinues early. Those subjects who discontinue study treatment in Cycle 1 transition to the Off-treatment Visit. Those who complete Cycle 1 will transition to the Extension Phase. Study treatment and tumor assessments will continue during the Extension Phase.

Phase 2 Cohorts

Once the MTD/RP2D of the combination of lenvatinib and everolimus in pediatric population has been determined in Phase 1, the Phase 2 portion of this pediatric study will commence with Cohort 1 (recurrent or refractory Ewing sarcoma/pPNET), Cohort 2 (recurrent or refractory rhabdomyosarcoma), and Cohort 3 (recurrent or refractory HGG), opening to accrual.

Cohorts 1 – 3

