Phase 2 Cohorts 1 to 3 will use a 10+10 Simon's optimal 2-stage design for each cohort; 10 evaluable subjects will be enrolled to each stage. The Sponsor will closely monitor enrollment to ensure that at least 50% of subjects enrolled in each cohort are <18 years of age at the time of informed consent. The primary outcome measure for Ewing sarcoma/pPNET, rhabdomyosarcoma, and HGG will be ORR (complete or partial response) at 16 weeks. If there are no responses among the 10 subjects in Stage 1, then the enrollment to that disease cohort will stop and conclude that the lenvatinib/everolimus combination therapy does not elicit a response in that disease cohort. If there is at least 1 response in the first stage, then the second stage will enroll 10 additional evaluable subjects. If there are 2 or fewer responses among the 20 evaluable subjects, then lenvatinib/everolimus combination therapy will be declared a failure for that disease cohort. Subjects will meet the criteria for being evaluable for an objective response if they have measurable disease present at baseline and at least 1 post-baseline efficacy assessment, unless they have discontinued prior to the first efficacy assessment due to progressive disease. Subjects who are not evaluable for objective response will be replaced.

The Treatment Phase for each subject in Phase 2 ends after completing 4 cycles of treatment unless subject discontinues early. Those subjects who discontinue study treatment before completing 4 cycles transition to the Off-treatment Visit. Those who complete 4 cycles will transition to the Extension Phase. Study treatment and tumor assessments will continue during the Extension Phase.

Dosing Nomogram

The dose nomogram in [Table 3](#) provides the dose of lenvatinib to be administered for BSA increments starting from 0.6 m². BSA must be calculated on Day 1 of each cycle based on the subject's current height and body weight. The actual dose to be administered is rounded to the nearest whole number. The total lenvatinib dose is capped at 18 mg daily (Dose Levels -1 and 1), and at 24 mg (Dose Levels 2 and 3).

Table 3 Total Lenvatinib Dose (mg): Body Surface Area (m²) * Dose Level (mg/m²)

Lenvatinib Dose Levels							
8 mg/m ² Everolimus 3.0 mg/m ² Dose Level -1		11 mg/m ² Everolimus 3.0 mg/m ² Dose Level 1		14 mg/m ² (Everolimus 3.0 mg/m ²) Dose Level 2		14 mg/m ² (Everolimus 4.5 mg/m ²) Dose Level 3	

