9.1.3 Extension Phase

All subjects who are still on study treatment following completion of Cycle 1 in Phase 1, or after completing 4 cycles in Phase 2 of the study, will transition to the Extension Phase. During the Extension Phase, subjects will continue to receive the same study treatment in 28-day cycles. Tumor assessments will be performed during the Extension Phase at Week 12 \pm 1 week and Week 24 \pm 1 week, and every 12 weeks \pm 1 week thereafter (Phase 1) and at Week 24 \pm 1 week, and every 12 weeks \pm 1 week thereafter (Phase 2).

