9.2 Discussion of Study Design

This multicenter, open-label, Phase 1/2 study will investigate safety, tolerability and antitumor activity of lenvatinib in combination with everolimus in pediatric subjects with relapsed or refractory solid tumors.

The Phase 1 portion of the study utilizes dose-finding rolling 6 design ([Skolnik, et al., 2008](#)), which allows enrollment of more than 3 subjects at the particular dose level, unlike the traditional 3+3 Phase 1 study design. If there is no DLTs in the first 3 subjects enrolled under rolling 6 design, then the fourth subject can be allocated to the next higher dose level. If toxicity data are not available on the first 3 subjects, or if one DLT is observed, in which

case the new subject will be kept at the same dose level. The main advantage of the rolling 6 design is the reduction of the overall study duration as it aims to decrease the number of times the study is suspended to accrual.

The Simon-optimal 2-stage design utilized for Phase 2 portion of the study allows for interim evaluation for futility. The traditional single-stage study designs evaluate drug response rate on the predetermined number of subjects, possibly unnecessarily exposing children to the risk of ineffective new agents. For ethical reasons, Simon's 2-stage design utilizes a small number of subjects to determine drug activity and allows early termination of the study if activity criteria are not met. This prevents exposure of too many pediatric subjects to an inactive study drug.

Toxicity will be assessed according to National Cancer Institute's CTCAE v4.03. In this study, the subjects will remain on treatment as long as they do not experience progression of disease or unacceptable toxicity. This will allow evaluation of short-term toxicity, as well as, side effects after prolonged use of combination of lenvatinib and everolimus, which is particularly important for pediatric population where physical growth and tissue maturation continues.

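### As worded, the ban on other investigational drugs ends when the Extension Phase begins, although the same study drugs continue

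*Protocol*

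**What the plan says.** Protocol Section 9.4.7.2 lists three groups of banned therapy: concurrent anticancer therapies, "Concurrent other investigational drugs", and live vaccines. The opening sentence sets the time limit: "Subjects are prohibited from receiving the following therapies during the Screening and Treatment Phase of this study".

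Section 9.1 fixes when the Treatment Phase ends. For Phase 1: "The Treatment Phase for each subject in Phase 1 ends after completing Cycle 1 of treatment unless subject discontinues early". For Phase 2: "The Treatment Phase for each subject in Phase 2 ends after completing 4 cycles of treatment unless subject discontinues early". Section 9.1.2 and footnote d of Tables 7 and 8 give the same lengths. Section 9.1.3 then says: "During the Extension Phase, subjects will continue to receive the same study treatment in 28-day cycles".

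Section 9.2 gives one reason for keeping subjects on treatment: it allows evaluation of "side effects after prolonged use of combination of lenvatinib and everolimus", which the protocol regards as especially important in children who are still growing.

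**The concern.** The ban is tied to a defined term that stops well before treatment does. Read as written, a subject who moves into the Extension Phase still takes lenvatinib and everolimus but is no longer under the ban.

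What is at stake is attribution of late adverse events. The prolonged-exposure safety data come largely from the Extension Phase, and the investigator judges causality event by event (Section 9.5.1.5.1). A second investigational agent taken at that time would make those judgements harder.

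**Working it through.** The plan states no statistical figure on this point. The check compares texts and then counts cycles.

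**1. Scope of the ban against the phase definitions**

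| Item | Where | Content |
|---|---|---|
| Time limit of the ban | 9.4.7.2, opening sentence | Screening and Treatment Phase |
| Treatment Phase, Phase 1 | 9.1, 9.1.2 | Cycle 1 |
| Treatment Phase, Phase 2 | 9.1, 9.1.2 | Cycles 1 to 4 |
| Later cycles | 9.1.3 | Extension Phase, same study drugs |

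The Extension Phase lies outside the stated limit.

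**2. Choice or slip?** The anticancer item exempts palliative radiotherapy as described in Section 9.4.7. That section says: "In the Phase 1 part, palliative radiotherapy will be allowed after the completion of Cycle 1". In Phase 1 the Treatment Phase is over by then, so the exemption does nothing unless the ban was meant to continue. This points to a slip.

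**3. What other rules cover in the Extension Phase**

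- *Anticancer therapy.* Section 9.4.7.2 treats additional anticancer therapy as evidence of progression and stops study drug, with no phase limit. Covered.
- *Live vaccines.* Their own entry in the list applies for as long as the subject is in the study. Covered.
- *Listed treatments needed for clinical management.* Section 9.4.7.2 requires discussion and agreement with the sponsor, with no phase limit. This is a consultation step, and it reaches only treatment the investigator judges necessary for managing the subject.
- *General medication rule.* Section 9.4.7 says that medication needed for the subject's health and "not expected to interfere with the evaluation of or interact with the study medication may be continued during the study". This permits some medication under conditions; it does not prohibit investigational drugs as such.
- *Drug interactions.* Section 9.4.7.1 deals with CYP3A4 and P-gp interactions, not with overlapping toxicity or attribution.
- *Elsewhere.* The synopsis text on concomitant therapy and the eligibility criteria (9.3.1, 9.3.2) contain no separate ban on investigational drugs.

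The remainder is mainly non-anticancer investigational drugs that are not taken for clinical management.

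**4. Share of treatment cycles outside the literal ban**

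For a subject treated for k cycles, the share is max(0, k − 4)/k in Phase 2 and (k − 1)/k in Phase 1.

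| k | Phase 2 | Phase 1 |
|---|---|---|
| 1 | 0% | 0% |
| 6 | 2/6 = 33% | 5/6 = 83% |
| 8 | 4/8 = 50% | 7/8 = 88% |
| 12 | 8/12 = 67% | 11/12 = 92% |

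In Phase 2 the share stays at 0% for anyone who stops by Cycle 4.

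The ceiling depends on how the estimated maximum of 24 cycles is read:

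- As total time on study (Section 9.1.6.1): Phase 2, 20/24 = 83%; Phase 1, 23/24 = 96%.
- As the Extension Phase alone (Section 9.1, Study Duration): Phase 2, 24/(4 + 24) = 24/28 = 86%; Phase 1, 24/(1 + 24) = 24/25 = 96%.

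**The case against.** The best defence is that the intended scope can be inferred and that little depends on the wording. The radiotherapy exemption makes sense only if the ban continues past Cycle 1. Tables 7 and 8 place all cycles under a top-level heading of Treatment. Section 9.4.1.3 uses Treatment Period for blood pressure monitoring that runs until control has lasted three consecutive months, which cannot fit into a 4-week phase. Anticancer therapy and live vaccines are handled elsewhere. The remaining case is hypothetical: a subject still on this combination takes a non-anticancer investigational drug that is not for clinical management, and nothing in the documents suggests that this is likely. Concomitant medications are recorded throughout (Table 8, footnote v), so co-exposure would be visible. The percentages cover all listed items together and do not measure exposure to the remaining risk. An amendment may also need regulatory and ethics review (Section 11.1) at about 60 sites.

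Much of this stands. A wider reading is possible, the gap is narrow, and the percentages show only how far the wording reaches. The gap is still open, however. The ban uses the defined term Treatment Phase, which the same tables set apart from the Extension Phase, and Treatment Period is a different term. Evidence that a wider scope was intended is a reason to correct the text. Recording co-exposure shows it afterwards but does not prevent it.

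**Conclusion.** The concern holds. As worded, the ban in Section 9.4.7.2 does not reach the Extension Phase, and no other provision expressly bans non-anticancer investigational drugs there. The wording should be corrected.

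The gain is small. It lies in protecting the attribution of late adverse events; no effect on the objective response rate is claimed. The conclusion rests on reading Treatment Phase as Section 9.1 defines it. The cycle shares also depend on how long a subject is treated, for which the documents give an estimated maximum but no distribution. How often another investigational drug would be taken is unknown. Confidence is high on the wording; the practical importance is modest.

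**What to change.** In Section 9.4.7.2, replace the time limit in the opening sentence with: *during Screening and throughout study treatment (Treatment and Extension Phases)*. The radiotherapy exemption then also has a function in Phase 1. Because subjects still on treatment at the final data cutoff continue dosing (Section 5.1), the correction can still take effect late in the study.

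The cost is one phrase in a protocol amendment, with whatever review Section 11.1 requires; it can travel with another amendment. It adds no procedures, visits or subjects, and the SAP needs no change for this point.
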